Index palbociclib treatment dose schedule change	MHS structured data	Treatment characteristic	Study observation period	Reported	Proportion of patients with dose changes
Date of treatment initiation	MHS structured data	Treatment characteristic	Study observation period	Not Reported	First date will be used if a regimen consists of more than one drug given on different dates.
Index treatment end date	MHS structured data	Treatment characteristic	Study observation period	Not Reported	Date of final treatment for each drug or regimen. It is possible that the patient's treatment stop date is not documented if the patient dies, is lost to follow up or is still on therapy. The final treatment date death date or end of

					study date will be used, whichever is earliest.
Variable	Source	Role in study	Period of measurement	Reporting phase	Operational definition
Post-palbociclib treatment duration	MHS structured data	Clinical Outcomes	Study observation period	Not Reported	
The regimen received by patients following discontinuation from the palbociclib treatment.
 
The duration (in weeks) between the start and stop of the post-palbociclib treatment. Findings will be summarized as the mean (\pm SD) and median (range) of values.

					subsequent treatment for unknown reasons
Time to chemotherapy after palbociclib treatment	MHS structured data	Clinical Outcomes	Study observation period	Reported	Time to chemotherapy (Kaplan Meier method median (95% CI)) from end of index treatment and start of chemotherapy. Summary of number of events and censored patients at 6, 12, 18, 24 months.
Time to next treatment (TTNT)	MHS structured data	Treatment characteristic	Study observation period	Reported	TTNT will be defined as the interval (in weeks or months) between the start of the index treatment date and the date of the next-line treatment. Patients who did not advance to the next treatment will be censored on the study end date or death, whichever occurs first. Kaplan-Meier (K-M) method with 95% CI and summary tables of

					events and censored patients at 6, 12, 18, 24 months.
CCI					

8.3.1. Demographic characteristics at baseline (from structured electronic database):

- Patient demographics: age, age group and gender.
- Region of residence (North, Central, South).

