- Number (N) (%) patients receiving first, second- and third-line treatments by drug name and therapeutic group, median duration of each line of therapy, and number of cycles for each line of therapy. Treatment lines are defined according to the sequence of dispensed medications, with information captured both from pharmacy database (for medications approved by the HMO), and from hospital medical records (including information on medications provided by private insurance and clinical studies) using the following algorithm. Any drug purchased within 1 month of a new line is considered part of that line. Cessation of a drug from a combination regimen is considered the same line as the patient is not receiving additional treatment. Cessation is likely due to tolerance issues or adverse effects although we do not know the reason as our data is from purchase data. Addition of a new drug to a current regimen is considered a new treatment line.
- Index treatment regimen - palbociclib combination partner: Aromatase Inhibitors (AI) or fulvestrant; Subsequent therapy per lines of therapy.
- Dosing and dose changes, interruptions, delays, and discontinuations associated with palbociclib therapy.
- Treatment lines will be rerun for extended follow up to 30 June 2022.

8.3.4. Cancer related variables:

These variables will be extracted from patient PDF files/ letters sent to MHS from the physician.

- Date of initial breast cancer diagnosis.
- Histology.
- Location of metastases: bones, brain, visceral, lymph nodes, other.

- ECOG performance status at diagnosis.
- Molecular status data: performed HER2/ HR tests (yes/no).
- Hormone sensitivity: primary or secondary resistance.
- Progression of disease from imaging.

8.3.5. Clinical outcomes for palbociclib (analysed separately by therapy line):

- N (%) progression at 6, 12 and 24 months.
- Duration of treatment on palbociclib (Median time on treatment).
- Time on treatment for subsequent line of therapy.
- Time to chemotherapy after palbociclib treatment.

■ CCI [REDACTED]

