8.7. Data analysis

Data will consist of structured data from the MHS electronic database and non-structured data extracted from PDF files of patient data. Data validation will be performed and consist of quality control checks for appropriate values, logical sequences and quantity of missing values. Missing data will be identified and reported in the results tables as percentages for all variables. If there is a large amount of missing or illogical data, a decision to include, exclude or impute that variable will be subsequently made based on the study sponsor's decision.

Descriptive analyses will be conducted to evaluate the demographic, clinical and treatment characteristics overall, as well as for each of the study cohorts. Results will be reported in aggregate. Categorical variables (eg, ECOG performance status) will be reported as frequency and percentage. Continuous variables such as age will be reported as mean, (standard deviation) and median (Inter quartile range). In the case of missing observations, the number and percentage of missing values will be reported. Chi-square testing will be used to assess associations between categorical variables when patient counts for single cells within the results tables are greater or equal to 5. When distribution cannot be assumed to be Chi-square, then Fisher's exact test will be used. Depending on normality, analysis of variance (ANOVA)/t-tests or Kruskall-Wallis tests will be used for continuous variables. An alpha level of 0.05 will be the primary criterion for statistical significance of this study.

Time from treatment initiation until progression (as determined in the patient record) and drug discontinuation will be determined for the calculation of median time on treatment.

Duration of treatment on palbociclib, Time on treatment for subsequent line of therapy and Time to chemotherapy after palbociclib treatment and **CCI**

Plots will be generated. Patients are censored at end of study or left MHS.

Sub- analyses will be carried out for palbociclib.

All analyses will be conducted using IBM SPSS Statistics for Windows, Version 22.0. Armonk, NY: IBM Corp, and a P value < 0.05 is considered statistically significant.

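### Time to chemotherapy after palbociclib is a second gap time cut off at a calendar date; if it is positively correlated with time on palbociclib, its Kaplan-Meier median reads too short

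*Combined protocol and SAP*

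**What the plan says.** The variables table in section 8.3 lists "Time to chemotherapy after palbociclib treatment" as a clinical outcome and defines it as "Time to chemotherapy (Kaplan Meier method median (95% CI)) from end of index treatment and start of chemotherapy". It adds a "Summary of number of events and censored patients at 6, 12, 18, 24 months". Section 8.3.5 lists the same outcome among those for palbociclib, to be analysed separately by therapy line.

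Three other rules bear on it:

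- **Censoring.** Section 8.7 states: "Patients are censored at end of study or left MHS". Death is not named for this outcome.
- **End of index treatment.** The table concedes: "It is possible that the patient's treatment stop date is not documented if the patient dies, is lost to follow up or is still on" (that is, still under treatment). It then takes the earliest of the final treatment, death and end-of-study dates ("study date will be used, whichever is earliest"). No rule says whether patients still on palbociclib, or who died on it, enter the time-to-chemotherapy analysis.
- **The neighbouring outcome.** Time to next treatment is "the interval (in weeks or months) between the start of the index treatment date and the date of the next-line treatment", so its clock starts at index. It is censored at study end or death.

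No chemotherapy-specific measure from index is visible. One clinical outcome is redacted in sections 8.3 and 8.3.5, as is part of the analysis sentence in section 8.7.

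**The concern.** Kaplan-Meier needs censoring that is unrelated to the outcome. Patients enter over 32 months and follow-up ends on one calendar date, so whatever time a patient spends on palbociclib is taken from the time available to observe the later interval. Patients who stop early are watched longest; those with long courses are watched briefly or not at all. If patients who do well on palbociclib also tend to remain chemotherapy-free for longer afterwards, the patients lost early are those with the better outlook.

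At stake are the reported median and the comparison between lines. Two lines with the same true post-palbociclib experience could show different medians only because palbociclib courses are longer in one of them. The plan neither assumes nor checks independence of the two durations, and no remedy is planned.

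**Working it through.** The plan gives no expected time to chemotherapy, event count or correlation, so there is no planned figure to reproduce. The check is structural, followed by simulation.

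**1. Structure.** Let T1 be time on palbociclib, T2 the time from palbociclib end to chemotherapy, and C the time from index to cut-off. The interval is seen only if T1 < C. Observed time is min(T2, C − T1), with an event if T2 ≤ C − T1. Staggered entry makes C unrelated to T2, but the effective censoring time C − T1 is unrelated to T2 only if T1 is.

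**2. Follow-up available.** Accrual from 1 January 2018 to 31 August 2020 (section 8.1) with cut-off 30 June 2022 gives C between 21.9 and 53.9 months. For the last patient to enter:
- 6 months on palbociclib leaves 21.9 − 6 = 15.9 months of observation;
- 18 months leaves 21.9 − 18 = 3.9 months.

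**3. Simulation.** From the plan: the accrual window and cut-off. Assumed: uniform entry, exponential T1 and T2, median T1 of 12 or 20 months, median T2 of 14 months, Gaussian-copula correlation, no deaths, 300,000 patients per scenario. Estimated median of T2 (true value 14 months), cut-off June 2022:

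| Correlation | Median T1 12 months | Median T1 20 months |
|---|---|---|
| 0 | 14.0 | 14.0 |
| 0.3 | 12.6 | 11.6 |
| 0.5 | 11.8 | 10.3 |

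Still on palbociclib at cut-off: 13% (median T1 12) and 28% (median T1 20).

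**4. Effect on by-line results.** T2 has the same true distribution in both columns, yet the estimates differ by 12.6 − 11.6 = 1.0 month at correlation 0.3 and 11.8 − 10.3 = 1.5 months at 0.5.

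**5. Other inputs.** With median T1 of 12, 20 or 28 months and the June 2022 cut-off, correlation 0.3 gives 6.3 to 7.3 months against a true 8, and 12.4 to 14.3 against a true 16. Correlation 0.6 gives 5.0 to 6.7 and 9.7 to 13.0. At zero correlation both are recovered.

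**6. Cut-off.** The extension to June 2022 is described for treatment lines and patterns (sections 7, 8.1 and 8.3.3), so it is unclear whether it covers this outcome. Subtracting the stated year and a half gives 31 December 2020. With that inferred cut-off, the step 3 estimates for correlations 0.3 to 0.5 fall to between 8.4 and 11.3 months.

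**7. Alternatives from index.** Without deaths, Kaplan-Meier of T1 + T2 from index matched the true median within 0.1 month wherever the median was reached. It was not reached in half of the step 5 scenarios with the December 2020 cut-off. With deaths added (assumed median 40 months from index, same correlation) and censored as for time to next treatment, it is biased upward. At correlation 0.3 and the June 2022 cut-off it gives about 34 against 30 months (median T1 12) and about 45.6 against 39 (median T1 20). Chemotherapy-free survival from index, with death as an event, matched the truth in every scenario. Adding deaths also makes the bias in the gap-time estimate smaller.

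**The case against.** **The outcome does what its name says.** It describes what follows palbociclib, and time on palbociclib is covered by median time on treatment and by time to next treatment from index. A reader might infer that the clock has been set at the wrong end and that the outcome is misdefined. The documents do not support that. A patient with 6 months on palbociclib and one with 36, each starting chemotherapy 3 months later, both count as 3 months (9 and 39 from index), but that is what a post-treatment interval is. The study is descriptive, with no comparator. This objection stands in full.

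**The bias is conditional.** The documents give no correlation, and at zero there is none. Analysis by line removes the between-line part. This stands too, but by-line analysis leaves dependence within a line, and the plan does not address it.

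**Censoring is already displayed.** Counts of events and censored patients at four time points will show heavy early censoring. They neither say that it may be related to prognosis nor correct for it.

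**Moving the clock is not enough.** If deaths are censored, the estimate from index is biased by the same kind of correlation, in the other direction. This stands and shapes the fix.

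**Patients still on treatment.** A reader might infer that they contribute nothing. The plan does not say so: the end-date rule can assign them an end date, and it is silent on whether that date starts the clock.

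**Conclusion.** The point holds in conditional form. Follow-up for this interval shrinks as time on palbociclib grows, and Kaplan-Meier is valid only if the two durations are unrelated within a line. Positive correlation is plausible in the same patient, and the median then reads too short: by about 1.4 to 2.4 months out of 14 at correlation 0.3 (14 − 12.6 and 14 − 11.6), and 2.2 to 3.7 at 0.5 (14 − 11.8 and 14 − 10.3). The larger figures belong to the longer palbociclib courses.

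These sizes rest on exponential times, no deaths, the June 2022 cut-off and medians that are not in the documents. They also impose no minimum time on palbociclib, whereas section 8.2.1 asks for at least 6 months of available palbociclib data, which could be read as a minimum course. The sizes are illustrations, not predictions. It would go too far to say that the reported median will be biased, or that the interval from palbociclib end should be dropped. The plan should be changed because it reports this outcome by line without a caveat, a rule for death or a rule for ongoing treatment.

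**What to change.** In sections 8.3, 8.3.5 and 8.7:

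1. Add time from index date to first chemotherapy in all index patients, by line. Treat death as a competing event (cumulative incidence) or count it as an event (chemotherapy-free survival). Do not censor it as time to next treatment does.
2. Keep the interval from palbociclib end as a supplementary description restricted to patients who actually stopped palbociclib, with numbers at risk and a statement that censoring may depend on time on palbociclib.
3. State that an end date assigned because of death or study end is not a discontinuation and does not start this clock.
4. State which data cut-off applies to this outcome.

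The cost is a few lines of text and one further analysis, using index and death dates already collected and the chemotherapy dates the present outcome already needs. There are two small downsides. The figure from index mixes time on palbociclib with later therapy, so both intervals should be shown. Its median may not be reached if an earlier cut-off applies, so percentages at fixed times should be reported as well.

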8. RESEARCH METHODS

8.1. Study design

This is a population based retrospective database study that will include patients with metastatic, HR+/ HER2- breast cancer and who initiated first or subsequent lines of treatment with palbociclib. Data will be available from Maccabi Healthcare Services (MHS) database in Israel for patients who received approval for treatment with palbociclib since 01 January 2018 until 31 August 2020.

Treatment amendment and extension: Treatment lines will be rerun for the same patient cohort for an additional year and a half of follow-up to 30 June 2022.

The database review followed by a medical record review will capture data from approximately 500-700 patients on demographics, clinical characteristics, disease history, treatment history, palbociclib dosing, clinical outcomes and post-palbociclib combination therapy treatment data. The study will be descriptive in nature therefore no control or comparator groups will be included.

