8.2. Setting

Patients (age \geq 18 years) will be identified from MHS purchase data between 01 July 2017 until 31 August 2020.

Index date will be defined as date of initiation of palbociclib treatment.

Patient records must meet the following criteria to be eligible for the medical record reviews. Patients must be at least 18 years of age at index date and they must have been diagnosed with HR+/HER2- ABC/ MBC. Patients must have received palbociclib combination in line with Israel approved indications. A minimum of 6 months follow up of palbociclib combination therapy prior to date of medical record review will be necessary for inclusion. This will permit the capture of meaningful clinical outcomes data. Patients will be followed through the end of the observation period, date of death or left the health maintenance organization (HMO).

A full list of the inclusion criteria can be found in Section 9.2.1.

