8.2.1. Inclusion criteria

Patients must meet all of the following inclusion criteria to be eligible for inclusion in the study:

1. A diagnosis of metastatic breast cancer, based on the National/MHS cancer registry.
2. Newly diagnosed metastatic breast cancer patients and newly treated with palbociclib within 6 months of diagnosis, in any line of treatment in the metastatic setting.
3. Available data on palbociclib treatment for at least 6 months.
4. Continuous healthcare plan enrolment in MHS for at least one year before index date.
5. At least 18 years of age at index date.

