Genetic testing for gBRCAm performed	MHS structured data	Baseline characteristic	Baseline	Reported	yes/no
Death	MHS structured data	Endpoint	After index date		Death is captured from National Insurance Data
Disease Characteristics					
Date of initial breast cancer diagnosis	National cancer registry	Baseline characteristic	Baseline	Reported	Records may be incomplete
Histology	Extracted from PDF patient data files	Baseline characteristic	Baseline	Reported	
Location of metastases	Extracted from PDF patient data files	Baseline characteristic	Baseline	Reported	Bone, brain, lymph nodes, ovary, visceral
Visceral/non visceral status	Extracted from PDF patient data files	Baseline characteristic	Baseline	Reported	Non-visceral, visceral (lungs, liver), bone only
Eastern Cooperative Oncology Group (ECOG) performance status at diagnosis	Extracted from PDF patient data files	Baseline characteristic	Baseline	Reported	Grouped as 0-1, 2, 3-4, unknown/missing
Molecular status data: performed HER2/ HR tests	Extracted from PDF patient data files	Baseline characteristic	Baseline	Reported	yes/no
Hormone sensitivity	Extracted from PDF patient data files	Baseline characteristic	Baseline	Reported	primary or secondary resistance
Variable	Source	Role in study	Period of measurement	Reporting phase	Operational definition
Progression of disease from imaging	Extracted from PDF patient data files	Baseline characteristic	Baseline	Reported	
Treatment Characteristics					

Index treatment regimen	MHS structured data	Treatment characteristic	Study observation period	Reported	Palbociclib combination treatment - combination with aromatase inhibitor or fulvestrant.
Lines of therapy	MHS structured data and PDF patient data files.	Treatment characteristic	Study observation period	Reported	Identified according to the sequence of dispensed medications.
Median duration of each line of therapy	MHS structured data	Treatment characteristic	Study observation period	Reported	Duration in weeks or months between the start and stop of each line of therapy will be reported as mean (SD) and median (IQR)
Number of cycles of index treatment	MHS structured data	Treatment characteristic	Study observation period	Reported	Mean (SD) and Median (IQR)
Index palbociclib treatment dose	MHS structured data	Treatment characteristic	Study observation period	Reported	Mean (SD) and Median (IQR)

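### TTNT is analysed by Kaplan-Meier with death as ordinary censoring, and time to chemotherapy has no death rule; with death censored, 1-KM overstates the share who start next treatment or chemotherapy

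*Combined protocol and SAP*

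**What the plan says.** In the 8.3 Variables table, TTNT runs from the start of index treatment to the start of the next line. The method is Kaplan-Meier with a 95% CI, and death is dealt with explicitly: "Patients who did not advance to the next treatment will be censored on the study end date or death, whichever occurs first". Next-line treatment is therefore the only event. The summary tables give events and censored patients at 6, 12, 18 and 24 months.

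The time-to-chemotherapy row reads: "Time to chemotherapy (Kaplan Meier method median (95% CI)) from end of index treatment and start of chemotherapy", followed by "Summary of number of events and censored patients at 6, 12, 18, 24 months". It says nothing about patients who die first.

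The three statements on the end of follow-up differ:

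- the TTNT row names study end and death;
- 8.7 says "Patients are censored at end of study or left MHS" and does not name death;
- 8.2 (Setting) ends follow-up at the end of observation, death or leaving the health plan.

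Death dates are available: "Death is captured from National Insurance Data". The visible text names no competing-risk method, defines no composite of next treatment or death, and does not say that a quantity conditional on nobody dying is intended. Part of the 8.7 sentence on these outcomes is redacted, and nothing here relies on what it may contain.

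**The concern.** Ordinary censoring assumes that the patient could still have the event later, at the same rate as those still under observation. That is reasonable for someone who reaches the data cut-off. It cannot hold for someone who has died. Kaplan-Meier in effect hands the deceased patient's remaining probability to the survivors, so 1-KM rises above the share of the cohort that starts a next line.

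The study is descriptive, and its objective in section 7 covers treatment patterns and clinical outcomes. Readers will take the curves and medians as what happened to these patients. All have metastatic disease and several therapy lines are included, so some deaths before the next line are to be expected. Time to chemotherapy is analysed by therapy line (8.3.5). If mortality differs by line, so does the bias, and the side-by-side description is distorted.

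The tables would also hide the cause. Under 8.1, "Treatment lines will be rerun for the same patient cohort for an additional year and a half of follow-up to 30 June 2022". If TTNT uses that cut-off, nobody is cut off administratively by month 18, and the censored column up to then holds only deaths and the few who leave the health plan.

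**Working it through.** The plan has no event rate, death rate or sample-size calculation, so there is no planned figure to reproduce. All rates below are assumptions, chosen to show direction and range.

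**Set-up.** Constant hazards: λ1 for next treatment, λ2 = r·λ1 for death first, with r = 0.10, 0.25, 0.50.

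- 1-KM with death censored: 1 − exp(−λ1·t)
- Cumulative incidence: CIF(t) = [1/(1+r)]·[1 − exp(−λ1(1+r)t)]
- Median from the CIF: −ln(1 − 0.5(1+r)) / [λ1(1+r)]
- Median with death counted as an event: ln 2 / [λ1(1+r)]

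**TTNT, assumed 18-month median** (λ1 = ln 2/18 = 0.0385 per month). At 24 months, 1-KM = 1 − 2^(−24/18) = 60.3%. For r = 0.25, CIF = 0.8·[1 − 2^(−30/18)] = 54.8%.

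| r | 1-KM, 24 mo | CIF, 24 mo | KM median | CIF median | Median, death as event |
|---|---|---|---|---|---|
| 0.10 | 60.3% | 58.0% | 18.0 | 18.9 | 16.4 |
| 0.25 | 60.3% | 54.8% | 18.0 | 20.4 | 14.4 |
| 0.50 | 60.3% | 50.0% | 18.0 | 24.0 | 12.0 |

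The death-censored median is too short as the time until half have started a next line, and too long as a median for next treatment or death.

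**Allowing for the 6-month requirement.** Inclusion criterion 3 in 8.2.1 is "Available data on palbociclib treatment for at least 6 months". If that removes every death before month 6, then for t > 6:

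CIF(t) = 1 − exp(−6λ1) + exp(−6λ1)·[1/(1+r)]·[1 − exp(−λ1(1+r)(t−6))]

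Overstatement by 1-KM, in percentage points:

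| r | 6 mo | 12 mo | 18 mo | 24 mo | CIF at 24 mo | CIF median | Median, death as event |
|---|---|---|---|---|---|---|---|
| 0.10 | 0 | 0.2 | 0.6 | 1.2 | 59.1% | 18.3 | 16.9 |
| 0.25 | 0 | 0.4 | 1.5 | 2.9 | 57.4% | 18.9 | 15.6 |
| 0.50 | 0 | 0.9 | 2.9 | 5.5 | 54.8% | 20.0 | 14.0 |

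**Shorter TTNT.** With an assumed 12-month median and no delay, 24-month 1-KM is 75.0% against 71.1%, 65.9% and 58.3%.

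**Time to chemotherapy, if deaths are censored.** Let s be the share of first events that are deaths, so r = s/(1−s). With an assumed 12-month Kaplan-Meier median, 24-month 1-KM is 75.0%. The CIF is 70.7%, 65.9%, 60.3% and 54.0% for s = 10%, 20%, 30% and 40%.

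**What the censored column would hold.** From 31 August 2020, the last entry date, to 30 June 2022 is 21.9 months, so the cut-off censors nobody at 6, 12 or 18 months. Take 600 patients, the middle of the expected 500–700, and the 18-month median. Deaths first by month 18 = 600·r·CIF(18):

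- r = 0.10: 600 × 0.10 × 0.485 = 29
- r = 0.25: 600 × 0.25 × 0.464 = 70
- r = 0.50: 600 × 0.50 × 0.431 = 129

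With no deaths before month 6 the counts are 17, 42 and 79. Section 8.4 puts departures below 1% a year, so leavers number fewer than 600 × 0.01 × 1.5 = 9.

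**Simulation check.** With r = 0.25, an 18-month median and staggered entry, Kaplan-Meier gave 60.3% and Aalen-Johansen 54.8% at 24 months, matching the formulas.

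**The case against.** The strongest reply is that death-censored Kaplan-Meier is a legitimate description of a cause-specific quantity, that the TTNT rule is explicit, and that the plan promises medians and counts rather than a 1-KM percentage. Raw event counts are unbiased, and 8.3.3 already reports the number and percentage receiving each line. That is fair as far as it goes. But the plan never says it wants the no-death quantity, the median carries the bias itself, and crude counts by line do not give incidence at a stated time.

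Second, the chemotherapy part is conditional. Its row does not say that deaths are censored, and 8.2 describes follow-up rather than a censoring list. The clock starts at the end of index treatment, which 8.3 may set to the date of death, so patients who die on palbociclib may add no time at risk. This stands: for that outcome the definite defect is the missing rule, and the bias follows only if death is censored. The 18-month follow-up argument is also confined to TTNT, since section 7 ties the extension to treatment patterns.

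Third, the size may be small. With the 6-month delay and r = 0.10 the gap is at most 1.2 points over the planned landmarks. This also stands, and it limits how serious the point is. It does not make an unstated target acceptable when the data to resolve it are in hand.

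**Conclusion.** The concern holds. For TTNT the plan as written gives a curve and median that overstate how many patients moved to a next line and how early. The direction is mathematical: the two estimates agree only if no death precedes the event. For time to chemotherapy the death rule is missing, and the same bias applies if death is censored.

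The size rests entirely on assumed rates and constant hazards. With an 18-month TTNT median the overstatement at 24 months runs from 1.2 points (r = 0.10, no deaths before month 6) to 10.3 points (r = 0.50, no delay). It is smaller at earlier landmarks and larger when the event comes sooner. This should be corrected before analysis, but it does not threaten the study as a whole.

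**What to change.** - For TTNT and time to chemotherapy, report Aalen-Johansen cumulative incidence at 6, 12, 18 and 24 months, with death before the event as a competing event.
- In the landmark tables, give deaths their own column, separate from censored patients.
- Put one sentence in both 8.3 and 8.7, for example: *Patients without the event are censored at the earlier of leaving MHS and the data cut-off; death before the event is a competing event.* Name the cut-off date for each outcome.
- State how patients whose index treatment ends at death enter the time-to-chemotherapy analysis.
- Keep the death-censored Kaplan-Meier curve as a labelled sensitivity analysis. If a treatment-benefit reading is wanted, add next treatment or death as a labelled composite.

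The cost is SAP wording and a few lines of code, with no new data. Section 8.6 lists R, but 8.7 says all analyses will be run in SPSS, so that sentence needs aligning. The reported shares starting next treatment or chemotherapy will come out lower.

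### The TTNT row does not censor patients when they leave MHS, although sections 8.2 and 8.7 do; the upward bias is small and one phrase removes it

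*Combined protocol and SAP*

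**What the plan says.** Four places in the plan bear on a patient who leaves MHS.

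- **Section 8.2 (Setting)**, general follow-up rule: "Patients will be followed through the end of the observation period, date of death or left the health maintenance organization (HMO").
- **Section 8.7 (Data analysis)**, censoring rule: "Patients are censored at end of study or left MHS". It comes just after a list of outcomes that visibly names time on palbociclib, time on the subsequent line and time to chemotherapy. One item in that list is blacked out.
- **Section 8.3, TTNT row**: "Patients who did not advance to the next treatment will be censored on the study end date or death, whichever occurs first". The row's source is MHS structured data. The output is a Kaplan-Meier estimate with counts of events and censored patients at 6, 12, 18 and 24 months.
- **Section 8.3, index treatment end-date row**: it notes that a stop date may be missing "if the patient dies, is lost to follow up or is still on therapy". It then takes the earliest of the final treatment date, death and study end ("study date will be used, whichever is earliest"). It lists no leaving date and does not say whether the resulting date is an event or a censoring time.

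**The concern.** A Kaplan-Meier estimate is valid only if patients counted as at risk could have had an event recorded. After a patient leaves MHS, a next-line purchase generally no longer reaches the data source. Under the TTNT row such a patient still counts as at risk and event-free until death or study end. The denominator is then too large while the numerator cannot grow, so the curve sits too high. The error always favours a longer TTNT, and extending follow-up to 30 June 2022 gives it more time to accumulate.

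The reported counts are affected as well. A patient who leaves event-free at month 10 belongs among the censored at months 12, 18 and 24. The row leaves that patient at risk at each of these times unless death comes first.

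There is also a reproducibility problem. One programmer working from section 8.3 and another working from sections 8.2 and 8.7 would produce different TTNT results.

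**Working it through.** The plan states no figure to reproduce: section 8.5 says that sample size calculations do not apply. The check compares the rules and then sizes the difference.

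**The rules side by side, for a patient who leaves event-free**

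| Place | Patient's time ends at |
|---|---|
| 8.2 | leaving |
| 8.7 | leaving |
| 8.3, TTNT row | death or study end |
| 8.3, end-date row | last recorded treatment; status not given |

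The last line follows because a recorded final treatment cannot fall after death or study end, so the earliest-of rule returns it.

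**Inputs**

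- Leaving rate: section 8.4 gives under 1% per year for the whole membership, with no figure for this cohort. I use 1%, so μ = 0.01/12 = 0.000833 per month.
- Index dates from 1 January 2018 to 31 August 2020 and study end on 30 June 2022 (section 8.1). Follow-up is therefore 21.9 to 53.9 months, mean 37.9 if accrual is uniform (assumed).
- N = 500 to 700 (section 8.5).
- Assumed: exponential TTNT with median 18 months, so λ = ln 2/18 = 0.03851 per month; leaving independent of TTNT; no deaths.

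**Step 1. How many leave.** Ignoring other events, 1 − exp(−0.01 × 37.9/12) = 3.1%, or about 16 to 22 patients. Leaving before a next line: [μ/(λ+μ)] × [1 − exp(−(λ+μ) × 37.9)] = 1.64%, or about 8 to 11 patients.

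**Step 2. TTNT at 24 months, leaving possible from month 0.**

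- Censoring at leaving: S(24) = exp(−24λ) = 0.3969.
- Row as written: S(24) = 1 − [λ/(λ+μ)] × [1 − exp(−24(λ+μ))] = 1 − 0.9788 × (1 − 0.3890) = 0.4019.
- Excess: 0.5 points. The same formula gives 0.05, 0.17 and 0.33 points at 6, 12 and 18 months.

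**Step 3. Leaving only after month 6.** Sections 8.2 and 8.2.1 require at least 6 months of follow-up or palbociclib data, so early leavers should be largely absent.

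- Row as written: S(24) = exp(−6λ) × {1 − 0.9788 × [1 − exp(−18(λ+μ))]} = 0.7937 × [1 − 0.9788 × (1 − 0.4926)] = 0.3995.
- Excess: 0.26 points. At 12 and 18 months it is 0.04 and 0.14 points.

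**Step 4. Misplaced patients at month 24.** From month 0: 0.0212 × (1 − 0.3890) = 1.29%, about 6 to 9 patients. After month 6 only: 0.7937 × 0.0212 × (1 − 0.4926) = 0.85%, about 4 to 6 patients. Both are slightly high, because the last entrants have under 24 months of follow-up.

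**Step 5. Sensitivity to the assumed median.** For true medians of 12, 18, 24 and 30 months with leaving from month 0, the row as written gives 12.1, 18.2, 24.3 and 30.5 months. The 24-month excess is then 0.4 to 0.6 points, or 0.2 to 0.3 points with leaving only after month 6. A simulation with administrative censoring uniform on 22 to 54 months agrees: for true medians of 12 and 24, censoring at leaving gives 11.9 and 24.0, and the row as written gives 12.0 and 24.3.

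**Step 6. Scale.** For a proportion near 0.40, the 95% half-width is 1.96 × √(0.4 × 0.6/N) = 4.3 points at N = 500 and 3.6 at N = 700. The bias is roughly a tenth of that or less.

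**Step 7. Time on palbociclib (conditional).** Only if a leaver's last recorded treatment were counted as a discontinuation would the hazard become λ+μ. A true 18-month median would then read as ln 2/0.03934 = 17.6 months.

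**The case against.** The strongest reply is that the general rules already cover TTNT. Section 8.2 ends follow-up for every patient at departure, the TTNT row is measured over the study observation period, and the censoring sentence in section 8.7 is not limited to particular outcomes. Because one item in the section 8.7 list is blacked out, TTNT's absence from the visible text proves little. A careful analyst would probably censor at leaving. This stands as a reason not to assume the worst reading will be programmed. It does not remove the conflict, because the TTNT row carries its own explicit and different rule.

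The second reply is size: the study is descriptive with no comparator, the bias lies well inside the sampling error, and nothing shows that a conclusion would change. That is correct. The no-death assumption also overstates the effect. Deaths come from National Insurance data, so they may still be seen after departure and would end the spurious follow-up earlier.

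A reader might go further and infer that the plan counts leavers as having discontinued palbociclib, so that time on treatment is biased downward while TTNT is biased upward. The documents do not support that. The end-date row sets a date and not an event status, section 8.7 visibly covers palbociclib duration and censors at leaving, and section 8.6 takes discontinuation from chart review. The gap in that row is one of clarity.

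**Conclusion.** The inconsistency is real. The TTNT row omits a censoring reason that both general rules include and, followed as written, keeps patients at risk when their next line generally cannot be seen. The consequence is a small upward bias in TTNT: about 0.3 to 0.5 points on the 24-month event-free proportion, 0.1 to 0.5 months on the median for assumed medians of 12 to 30 months, and a handful of misplaced patients in the 24-month count.

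These figures rest on a 1% annual leaving rate, an exponential TTNT, independent leaving and no deaths. The rate is a bound for the whole membership. If this cohort leaves faster, the bias grows roughly in proportion; the documents give no reason to assume that it does.

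The point is worth correcting because the rule is contradictory and the correction costs almost nothing. The end-date row is a secondary matter: time on treatment would be affected only if the last recorded treatment date were counted as a discontinuation, which the plan does not say.

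**What to change.** 1. Section 8.3, TTNT row: change the rule to *censored at the earliest of study end, death or date of leaving MHS*. The handling of death in that row is unchanged by this point.
2. Section 8.7: state that censoring at leaving applies to every time-to-event outcome, including TTNT.
3. Section 8.3, index treatment end-date row: state that a patient still on palbociclib when leaving MHS is censored and not counted as discontinued, so that the row agrees with section 8.7. Time to chemotherapy starts from this end date, so the row should be settled before that outcome is programmed.

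The cost is a phrase in two rows of section 8.3 and a scope sentence in section 8.7. The leaving date is already needed for sections 8.2 and 8.7, so no new data are required.
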